Efficacy assessments	
 • Neutrophil count • Reticulocyte count • Platelet count • Hemoglobin • Use of immunosuppressive therapy • Use of platelet transfusions • Use of red blood cell transfusions • Bone marrow biopsy
Safety assessments	
 • Cyclosporine levels • Flow cytometry of peripheral blood for GPI-cells • Adverse events • ECG • Bone Marrow for clonal evolution
Other assessments	
 • Full PK profile over 8 hours at 2 weeks and trough samples at 1 month, 2 months, 3 months, and 6 months
Data analysis	
50 patients will be enrolled in the study.
 
Data will be analyzed at two important time points 6 and 24 months:
 
 • The primary analysis will be done on all the patients enrolled who have completed 6 months or discontinued prior to 6 months. • The final analysis will be done on the responders who have completed 24 months or

[figure not shown]

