2.6 Risks and benefits

SAA is considered a rare disorder, which can be, life threatening if untreated. Without effective treatment, patients with SAA have a life expectancy of 1 to 2 years after diagnosis due to fatal infections or hemorrhagic complications.

The current options for effective treatment for SAA are HSCT or IST. However, HSCT is available to only a minority of patients, and about half of patients who receive IST as a first line therapy fail to achieve hematologic response and experience relapse or clonal evolution associated with myelodysplasia and leukemia.

No new or unexpected safety signals were observed in studies conducted in SAA patients, in both refractory and first-line indications.

The safety profile of eltrombopag up to 150 mg alone or in combination with h-ATG and CsA is acceptable and consistent with the prescribing information (for all 3 drugs), in light of the underlying population with SAA. No new or unexpected safety signals were observed. The risk specific to patients with SAA is the potential for cytogenetic abnormalities. The role of eltrombopag in the development of cytogenetic abnormalities remains unknown. The development of cytogenetic abnormalities is a known risk for patients with SAA and part of the natural history of the underlying disease. The incidence of clonal evolution observed in the refractory studies (ETB115AUS18T and ETB115AUS28T) and in the pivotal study (ETB115AUS01T) in IST-naive SAA patients is consistent with what has been reported in the historical data. A final conclusion about the early onset of cytogenetic abnormalities relative to SAA, immunosuppression treatment or eltrombopag cannot be made. Bone marrow examination including cytogenetics will be performed as described in [Section 7.2.4](#) and [Table 7-1](#). Development of new cytogenetic abnormalities will result in permanent discontinuation of investigational treatment as described in [Section 6.3.1.2](#).

The risks to patients in this study may come from adverse events and lack of efficacy (described in [Section 1.2.1.2.2](#), [Section 1.2.1.2.3](#), [Section 8.1](#) and [Section 8.1.3](#)).

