4. To evaluate the clonal evolution to myelodysplasia, paroxysmal nocturnal hemoglobinuria (PNH), and leukemia	Percentage of patients with evolution to myelodysplasia, PNH, and acute leukemia occurring at any time during the study	
5. To evaluate red blood cells (RBC) transfusion independence	Percentage of patients who are RBC transfusion independent at least once by 6 months and by 24 months. Independence defined as no RBC transfusion for at least 56 days	
6. To evaluate platelet transfusion independence	Percentage of patients who are platelet transfusion independent at least once by 6 months and by 24 months. Independence defined as no platelet transfusion for at least 28 days.	
7. To evaluate the longest interval without a platelet or RBC transfusion	Duration of longest interval without a platelet transfusion by 6 months and by 24 months Duration of longest interval without a RBC transfusion by 6 months and by 24 months	
8. To evaluate the effect of Eltrombopag and cyclosporine on patient symptoms and health related quality of life	Change in scores from baseline to 6 months and 24 months on the FACT-G, FACT-TH18, and FACT-Fatigue scales	

Objective	Endpoint	Analysis
9. To evaluate the safety and tolerability of eltrombopag + cyclosporine	Safety will be assessed by: 
• Frequency and severity of AEs, serious AEs (SAEs) based on the Common Terminology Criteria of Adverse Events (CTCAE version 4. 03), and AEs leading to discontinuation, and evaluating changes in laboratory values within 6 months and within 24 months (responders only)• Incidence of the following adverse events of special interest	Refer to Section 10.5.3
10. To characterize the PK of eltrombopag when combined to cyclosporine	Plasma PK parameters of eltrombopag 2 weeks and trough concentrations at 1 month 1, 2 months, 3 months, and 6 months	Refer to Section 10.5.4

Objective	Endpoint	Analysis
*Overall hematologic response = patients with complete response (CR) + patients with partial response (PR)		
a. Partial response is defined as any two of the following parameters at two consecutive, scheduled visit measurements at least 7 days apart during the study and no platelet transfusions within 7 days of platelet measurement (can still be a responder if ANC and reticulocyte measurements are valid):		

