5.3 Exclusion criteria

Patients eligible for this study must not meet **any** of the following criteria:

1. Diagnosis of Fanconi anemia.
2. Evidence of a clonal hematologic bone marrow disorder on cytogenetics by central review.
3. Prior immunosuppressive therapy with cyclosporine, alemtuzumab, rabbit or horse ATG and thrombopoietin receptor (TPO-R) agonists.
4. a. Hypersensitivity to eltrombopag or cyclosporine or their components.
b. Contraindications to cyclosporine.
5. AST or ALT >3 x ULN.
6. Serum creatinine, total bilirubin, or alkaline phosphatase >1.5 x ULN.
7. Patient with liver cirrhosis.
8. a. Infection not adequately controlled with appropriate therapy.
b. Patients who are human immune deficiency virus (HIV), hepatitis C virus or hepatitis B surface antigen (HBsAg) positive. HCV-RNA negative patients are allowed to be enrolled.
9. Moribund status or concurrent hepatic, renal, cardiac, neurologic, pulmonary, infectious, or metabolic disease of such severity that it would preclude the patient's ability to consent, be compliant with study procedures, tolerate protocol therapy, or patients with less than 3 months of life expectancy.
10. Patients with cancer who are not considered cure, are on active chemotherapeutic treatment or who take drugs with hematological effects.
11. Administration of an investigational drug within 30 days or 5 half-lives, whichever is longer, preceding the first dose of study treatment.
12. Pregnancy statements and contraception requirements:

Pregnancy or nursing (lactating) women

Women of child-bearing potential, defined as all women physiologically capable of becoming pregnant (or female partners of male patients), **unless** they are using highly effective methods of contraception during dosing and for 3 months after stopping medication. Highly effective contraception methods include:

- Total abstinence (when this is in line with the preferred and usual lifestyle of the patient. Periodic abstinence (e.g., calendar, ovulation, symptothermal, post-ovulation methods) and withdrawal are not acceptable methods of contraception)
- Female sterilization (have had surgical bilateral oophorectomy with or without hysterectomy), total hysterectomy, or tubal ligation at least six weeks before taking study treatment. In case of oophorectomy alone, only when the reproductive status of the woman has been confirmed by follow up hormone level assessment

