4. Action taken with respect to study treatment (none, dose adjusted, temporarily interrupted, permanently discontinued, unknown, not applicable)
5. Whether medication or therapy was given (no concomitant medication/non-drug therapy, concomitant medication/non-drug therapy)
6. Whether it is serious, where a Serious Adverse Event (SAE) is defined as in Section 8.2.1 and which seriousness criteria have been met
7. Outcome (not recovered/not resolved, recovered/resolved, recovering/resolving, recovered/resolved with sequelae, fatal, unknown)

If the event worsens the event should be reported a second time in the eCRF noting the start date when the event worsens in toxicity. For grade 3 and 4 adverse events only, if improvement to a lower grade is determined a new entry for this event should be reported in the eCRF noting the start date when the event improved from having been Grade 3 or Grade 4.

All adverse events should be treated appropriately. If a concomitant medication or non-drug therapy is given, this action should be recorded on the Adverse Event eCRF.

Once an adverse event is detected, it should be followed until its resolution or until it is judged to be permanent, and assessment should be made at each visit (or more frequently, if necessary) of any changes in severity, the suspected relationship to the study treatment, the interventions required to treat it, and the outcome.

Progression of malignancy (including fatal outcomes), if documented by use of appropriate method (for example, as per RECIST criteria for solid tumors or as per Cheson's guidelines for hematological malignancies), should not be reported as a serious adverse event.

Adverse events separate from the progression of malignancy (example, deep vein thrombosis at the time of progression or hemoptysis concurrent with finding of disease progression) will

be reported as per usual guidelines used for such events with proper attribution regarding relatedness to the drug.

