8.2.2 Reporting

To ensure patient safety, every SAE, regardless of suspected causality, occurring after the patient has provided informed consent and until at least 30 days after the patient has stopped study treatment must be reported to Novartis within 24 hours of learning of its occurrence.

Any additional information for the SAE including complications, progression of the initial SAE, and recurrent episodes must be reported as follow-up to the original episode within 24 hours of the investigator receiving the follow-up information. An SAE occurring at a different time interval or otherwise considered completely unrelated to a previously reported one should be reported separately as a new event.

Any SAEs experienced after the 30 day safety evaluation follow-up period should only be reported to Novartis if the investigator suspects a causal relationship to the study treatment.

Information about all SAEs is collected and recorded on the Serious Adverse Event Report Form; all applicable sections of the form must be completed in order to provide a clinically thorough report. The investigator must assess and record the relationship of each SAE to each specific study treatment (if there is more than one study treatment), complete the SAE Report Form in English, and submit the completed form within 24 hours to Novartis. Detailed instructions regarding the SAE submission process and requirements for signatures are to be found in the investigator folder provided to each site

Follow-up information is submitted in the same way as the original SAE Report. Each re-occurrence, complication, or progression of the original event should be reported as a follow-up to that event regardless of when it occurs. The follow-up information should describe whether the event has resolved or continues, if and how it was treated, whether the blind was broken or not, and whether the patient continued or withdrew from study participation.

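### A sentence carried over from oncology protocols exempts progression of malignancy, including death, from SAE reporting in a severe aplastic anemia trial, and conflicts with the SAE definition in Section 8.2.1

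*Protocol*

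**What the plan says.** Protocol Section 8.1.1 addresses "Progression of malignancy (including fatal outcomes), if documented by use of appropriate method" and says that it "should not be reported as a serious adverse event". As documentation methods it offers "for example, as per RECIST criteria for solid tumors" and a guideline for hematological malignancies. The next paragraph keeps events separate from the progression, such as a thrombosis at the same time, under the usual reporting rules.

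Other sections bear on this:

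- **Who can enrol (Section 5.3).** Criterion 2 excludes clonal marrow disorder on centrally reviewed cytogenetics. Criterion 10 excludes "Patients with cancer who are not considered cure, are on active chemotherapeutic treatment".
- **What is watched.** Secondary objective 4 in Table 3-1 is "Percentage of patients with evolution to myelodysplasia, PNH, and acute leukemia occurring at any time during the study". The protocol summary lists "Bone Marrow for clonal evolution" among the safety assessments. Section 2.6 states: "The risk specific to patients with SAA is the potential for cytogenetic abnormalities". Section 6.3.4 names progression of MDS as a concern for this class of drug.
- **General SAE rules.** Section 8.2.1 counts fatal and life-threatening events as serious. Section 8.2.2 requires "every SAE, regardless of suspected causality", from consent until at least 30 days after treatment stops, to reach the sponsor within 24 hours.

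**The concern.** An exemption of this kind suits a trial in which progression of a cancer is the disease course under treatment and is measured as an efficacy outcome. Here no patient should enter with an active malignancy, so a malignancy that progresses on study is in most cases a new event and a possible harm. The protocol leaves the role of eltrombopag in cytogenetic abnormalities open (Section 2.6) and says that cyclosporine raises the risk of lymphoma and other malignancies (Section 1.2.2.2.1).

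At stake is how fast and how uniformly such events reach the sponsor. There is no data monitoring committee (Section 8.6). The steering committee's stated safety review falls before the primary analysis (Section 8.7), while responders stay on cyclosporine up to 24 months. The sponsor's onward reporting to authorities, described in Section 8.2.2, starts from SAE reports. Two sites following different sections could handle the same death differently.

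**Working it through.** The plan states no figure on this point, so the check is to read the sections against each other, event by event.

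| Event on study | Section 8.1.1 | Sections 8.2.1 and 8.2.2 | Result |
|---|---|---|---|
| First diagnosis of MDS or AML | Not literally covered, since this is onset and not progression | SAE if a seriousness criterion is met | Agree |
| MDS found on study, then progressing to AML | Not an SAE | SAE if life-threatening, medically significant or otherwise serious | Conflict |
| Death from leukemia that arose on study | Not an SAE, because fatal outcomes are named | SAE, because fatal | Direct conflict |
| Progression of another new malignancy, or relapse of a cured cancer if read as progression | Not an SAE | SAE if a seriousness criterion is met | Conflict |
| Separate event at the time of progression | Usual rules | Usual rules | Agree |

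**Does Section 8.2 contain a matching exception?** Section 8.2.1 lists its own exceptions: certain hospitalizations, and emergency outpatient treatment that meets no seriousness criterion. Malignancy is not among them, and Section 8.2.2 does not refer back to Section 8.1.1.

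**Does any section limit the exemption?** None says that evolution to MDS or AML, or death from it, falls outside the exemption. The reference to a hematological-malignancy guideline points the other way.

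**What is recorded regardless of SAE status?**

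- Section 8.1.1 provides a Death form for all deaths and asks for a worsened adverse event to be entered again.
- SAP Section 2.7.1 tabulates deaths, and SAP Section 2.7.2 lists them for all screened patients.
- SAP Section 2.6.4 derives clonal evolution from the cytogenetics, flow cytometry and marrow pages, with listings reviewed by clinical and/or steering committee members.

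What remains exposed is the 24-hour report and the entry in the SAE tables of SAP Section 2.7.1.

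**Can the number of patients be estimated?** The nearest figure is clonal evolution in the earlier first-line study with h-ATG (Section 1.2.1.2.3): 15/154 = 9.7%. Applied to the 54 enrolled, 54 × 15/154 = 5.3. The historical range of 10–15% in Section 6.3.4 gives 54 × 0.10 = 5.4 to 54 × 0.15 = 8.1. These count clonal evolution, not malignancy that then progresses or kills, and they leave out other malignancies. The documents give no rate for the events that the exemption covers.

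**The case against.** The strongest reply is that a specific exception to a general rule is not a contradiction. Section 8.2.2 governs events that are SAEs, and Section 8.1.1 says that this one is not reported as such. On Section 8.2.2 alone that is fair. It does not answer Section 8.2.1, which defines fatal and life-threatening events as serious, lists its exceptions, and does not include this one.

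The second reply is that little is lost. Deaths and clonal evolution are captured and displayed by the routes listed above, and the exemption removes SAE reporting only, not the adverse event record. This stands and sets the size of the point. The adverse-event-of-special-interest route does not close the gap: Section 8.1.3 says only that rapid communication may be appropriate, and leaves the detail to the Investigator's Brochure.

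A reader might infer more than the documents support:

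- **That new MDS or AML is itself exempt.** The wording covers progression. A site might stretch it to evolution into leukemia, but the text does not say so.
- **That MDS and AML are the only possible targets.** Criterion 10 allows cured cancers, which could relapse, and cyclosporine carries its own malignancy risk.
- **That about 5 of 54 patients are affected.** That figure counts all clonal evolution. Protocol Section 10.5.1 counts a new cytogenetic abnormality even without dysplasia, and Section 1.2.1.2.3 describes new abnormalities in another study, none of them a malignancy. The rate also comes from a different regimen, and non-responders here leave after 6 months plus 30 days.
- **That clonal evolution is the trial's whole safety question.** It is one of ten secondary objectives. General safety is objective 9, and the SAP analyses clonal evolution among the secondary efficacy objectives.

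**Conclusion.** The point holds in a limited form. The exemption in Section 8.1.1 does not fit this disease. It conflicts with Section 8.2.1, and through it with the 24-hour duty in Section 8.2.2, for progression of or death from a malignancy that will in most cases have arisen on study. Progression of MDS is among the covered events and is a class concern that the protocol itself names.

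The consequence is delayed or uneven expedited reporting and possibly incomplete SAE tables. It is not loss of the deaths or of the clonal evolution endpoint. The primary response analysis is untouched. The number of events cannot be stated and may be small. The conclusion assumes that sites follow Section 8.1.1 as written and that no document outside the protocol and SAP, such as site SAE instructions or the Investigator's Brochure, overrides it.

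**What to change.** Delete the sentence in Section 8.1.1 that exempts progression of malignancy. The paragraph after it is not an exemption but refers to the deleted idea, so reword it to stand alone. Add one statement that new MDS, AML or other malignancy, and its progression or fatal outcome, are assessed and reported under Sections 8.2.1 and 8.2.2.

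The cost is wording in a protocol amendment, with the approvals in Section 12.1, and a few more SAE reports. Enrolment was complete when the SAP was written, so an amendment would reach only patients still in follow-up. For earlier events, checking the Death form and marrow data against the SAE reports would show whether any had been withheld.

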8.1.2 Laboratory test abnormalities

8.1.2.1 Definitions and reporting

Laboratory abnormalities that constitute an adverse event in their own right (are considered clinically significant, induce clinical signs or symptoms, require concomitant therapy or require changes in study treatment), should be recorded on the Adverse Events eCRF. Whenever possible, a diagnosis, rather than a symptom should be provided (e.g. anemia instead of low hemoglobin). Laboratory abnormalities that meet the criteria for adverse events should be followed until they have returned to normal or an adequate explanation of the abnormality is found. When an abnormal laboratory or test result corresponds to a sign/symptom of an already reported adverse event, it is not necessary to separately record the lab/test result as an additional event.

Laboratory abnormalities, that do not meet the definition of an adverse event, should not be reported as adverse events. A Grade 3 or 4 event (severe) as per CTCAE does not automatically indicate a SAE unless it meets the definition of serious as defined below and/or as per investigator's discretion. A dose hold or medication for the lab abnormality may be required by the protocol in which case the lab abnormality would still, by definition, be an adverse event and must be reported as such.

8.1.3 Adverse events of special interest

Adverse events of special interest (AESI) are defined as events (serious or non-serious) which are ones of scientific and medical concern specific to the sponsor's product or program, for which ongoing monitoring and rapid communication by the investigator to the sponsor may be appropriate. Such events may require further investigation in order to characterize and understand them.

Adverse events of special interest are defined on the basis of an ongoing review of the safety data. AESIs are discussed in detail in the Investigator's Brochure.

8.2 Serious adverse events

8.2.1 Definitions

Serious Adverse Event (SAE) is defined as one of the following:

- Is fatal or life-threatening
- Results in persistent or significant disability/incapacity
- Constitutes a congenital anomaly/birth defect
- Is medically significant, i.e., defined as an event that jeopardizes the patient or may require medical or surgical intervention to prevent one of the outcomes listed above
- Requires inpatient hospitalization or prolongation of existing hospitalization,
- Note that hospitalizations for the following reasons should not be reported as serious adverse events:

- Routine treatment or monitoring of the studied indication, not associated with any deterioration in condition
- Elective or pre-planned treatment for a pre-existing condition that is unrelated to the indication under study and has not worsened since signing the informed consent
- Social reasons and respite care in the absence of any deterioration in the patient's general condition
- Note that treatment on an emergency outpatient basis that does not result in hospital admission and involves an event not fulfilling any of the definitions of a SAE given above is not a serious adverse event

8.2.2 Reporting

To ensure patient safety, every SAE, regardless of suspected causality, occurring after the patient has provided informed consent and until at least 30 days after the patient has stopped study treatment must be reported to Novartis within 24 hours of learning of its occurrence.

Any additional information for the SAE including complications, progression of the initial SAE, and recurrent episodes must be reported as follow-up to the original episode within 24 hours of the investigator receiving the follow-up information. An SAE occurring at a different time interval or otherwise considered completely unrelated to a previously reported one should be reported separately as a new event.

Any SAEs experienced after the 30 day safety evaluation follow-up period should only be reported to Novartis if the investigator suspects a causal relationship to the study treatment.

Information about all SAEs is collected and recorded on the Serious Adverse Event Report Form; all applicable sections of the form must be completed in order to provide a clinically thorough report. The investigator must assess and record the relationship of each SAE to each specific study treatment (if there is more than one study treatment), complete the SAE Report Form in English, and submit the completed form within 24 hours to Novartis. Detailed instructions regarding the SAE submission process and requirements for signatures are to be found in the investigator folder provided to each site

Follow-up information is submitted in the same way as the original SAE Report. Each re-occurrence, complication, or progression of the original event should be reported as a follow-up to that event regardless of when it occurs. The follow-up information should describe whether the event has resolved or continues, if and how it was treated, whether the blind was broken or not, and whether the patient continued or withdrew from study participation.

If the SAE is not previously documented in the Investigator's Brochure or Package Insert (new occurrence) and is thought to be related to the Novartis study treatment, an oncology Novartis Chief Medical Office and Patient Safety (CMO&PS) department associate may urgently require further information from the investigator for Health Authority reporting. Novartis may need to issue an Investigator Notification (IN), to inform all investigators involved in any study with the same drug that this SAE has been reported. Suspected Unexpected Serious Adverse Reactions (SUSARs) will be collected and reported to the competent authorities and relevant ethics committees in accordance with Directive 2001/20/EC or as per national regulatory requirements in participating countries.

